The primary efficacy endpoint is the proportion of subjects who achieve at least a 75% improvement from baseline in the total modified Nail Psoriasis Severity Index (mNAPSI). The key secondary efficacy endpoint is the proportion of subjects with a score of "0 - normal" or "1 – minimal nail psoriasis" and at least a 2-point decrease from baseline at Week 28 as measured by the ViSENPsO. For each endpoint, the tildrakizumab 100 mg dose will be compared with the placebo at Week 28. Both the primary and key secondary efficacy endpoints will be analyzed using the Cochran-Mantel-Haenszel (CMH) test, incorporating prior use of TNF-alpha inhibitors and baseline body weight as stratifications factors. In addition, the Miettinen and Nurminen (M&N) common risk (the response rate) difference between tildrakizumab 100 mg and placebo arm, along with the 95% confidence interval (CI) will be estimated. The analyses will be based on the Intent-to-treat (ITT) population. All analyses will also be conducted for the Per Protocol Set (PPS) populations as supportive.

Efficacy hypothesis testing will be controlled for multiplicity using a step-down sequential testing approach for the primary and key secondary endpoints. If the test on the primary endpoint is significant at the alpha = 0.05 level, then the test comparing the key secondary endpoint between treatment arms will also be conducted at the 0.05 level. The subsequent test will not be conducted if the null hypothesis of the previous test is not rejected.

Secondary and exploratory efficacy endpoints obtained from Week 28 to Week 52 will be evaluated using summary statistics.

Safety endpoints will be analyzed descriptively based on the safety analysis set (SAF), defined as all subjects who received at least 1 dose of study treatment. Subjects will be summarized based on the actual treatment they received.

Intent-to-Treat (ITT): All randomized subjects who were dispensed study treatment, regardless of whether treatment was taken by the subject or not. The primary efficacy population will be the ITT.

[figure not shown]
Per Protocol Set (PPS): All subjects in the ITT population who complete the 28-week placebocontrolled treatment without any major protocol deviations.

Safety Analysis Set: All randomized subjects who have taken at least one dose of study treatment, based on the treatment received.

Sample Size Determination:

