9.4.1 Efficacy Analyses

Table 6: Efficacy Analyses

Endpoint Statistical Analysis Methods Primary and Key Secondary Efficacy Endpoints

The proportion of subjects who achieve at least a 75% improvement from Baseline in total modified Nail Psoriasis Severity Index

total modified Nail Psoriasis Severity Index (mNAPSI) at Week 28. (Primary efficacy endpoint)

• The proportion of subjects with a score of "0 - normal" or "1 – minimal nail psoriasis" and at least a 2-point decrease from baseline at Week 28 as measured by the ViSENPsO. (Key secondary endpoint)

The primary and key secondary analyses will be a comparison between the responders at Week 28 across the tildrakizumab 100 mg and placebo treatment arms using a Cochran-Mantel-Haenszel test, incorporating prior use of TNF-alpha inhibitors (yes/no) and Baseline body weight (≤90 kg or >90 kg) as stratification factors. In addition, M&N common risk (the response rate) difference between tildrakizumab 100 mg and placebo arm along with the 95% confidence interval will be estimated. These analyses will be based on the ITT population. All analyses will also be conducted for the PPS populations as supportive.

For the primary endpoint, subjects with missing values will be imputed using non-responder imputation. The estimand framework for the primary and key secondary efficacy endpoints will be based on composite strategy approach and details will be described in the SAP. The following sensitivity analyses will be performed:

- PPS, using Observed Cases only.
- Other sensitivity analyses based on multiple imputation methods, in addition to a tipping point analysis, will be described in the SAP.

Secondary and Exploratory Endpoints

- The proportion of subjects with, at least 3
 point decrease from Baseline in nail pain NRS
 score at Week 28 in subjects with baseline nail
 pain NRS score of > 3*
- The proportion of subjects achieving totalfingernail mNAPSI 90, and mNAPSI 100 at Week 28.
- The proportion of subjects achieving total fingernail NAPSI 75, NAPSI 90 and NAPSI 100 at Week 28
- Change in total-fingernail mNAPSI score from Baseline at Week 28.

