All secondary and exploratory efficacy endpoints will be analyzed using the ITT population. Binary endpoints up to Week 28 will be analyzed based on the methods described for the primary endpoint. For change-from-baseline at Week 28 (continuous), secondary efficacy endpoints, MMRM model with treatment, visit (Weeks 4, 8,12,16,20,24,28), prior use of TNF-alpha inhibitors (yes/no), baseline body weight (≤90 kg or >90 kg), treatment-by-visit interaction as factors and corresponding baseline value as a covariate will be performed. Secondary and Exploratory efficacy endpoints obtained from

Endpoint	Statistical Analysis Methods
Change in total-fingernail NAPSI score from Baseline at Week 28.	Week 28 to Week 52 will be evaluated using summary statistics.
Change in patient-reported nail pain NRS score	summary statistics.
Clinician-assessed proportions of ViSENPsO category results at Week 28 compared between treatment groups.	
• The proportion of subjects achieving PASI 75, PASI 90, and PASI 100 at Week 28.	
• The proportion of subjects achieving a PGA-S score of "clear" or "almost clear" with at least 2-point reduction from Baseline at Week 28.	
Percentage change in total BSA involvement from Baseline at Week 28.	
• Change from Baseline in mNAPSI, NAPSI, Nail Pain NRS, BSA, PGA-S, s-PGA, PASI and the proportions of ViSENPsO category results at measured time points through Week 52.	
Change from Baseline in DLQI score (total and domain scores), NAPPA-QoL score, CGIC, CGIS, PGIC, PGIC-P, PGIS, and PGIS-P at measured time points through Week 52.	
The proportion of subjects with, at least, 30% decrease in Nail Pain NRS score from Baseline at Week 28 in subjects with a baseline nail pain NRS score of > 3	

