9.1.3 Analysis of Primary Efficacy Endpoint

The primary efficacy endpoint of mNAPSI75 response at Week 28 will be analyzed using the ITT Set. A Cochran-Mantel-Haenszel (CMH) test will be performed stratified by body weight class (≤90 kg or >90 kg) and prior exposure to TNF-alpha inhibitors (Yes/No) for psoriasis. Common proportion difference between the treatments and the associated 95% confidence interval will be calculated using Miettinen-Nurminen (M-N) stratified body weight class (≤90 kg or >90 kg) and prior exposure to TNF-alpha inhibitors (Yes/No). The p-value from the CMH test comparing tildrakizumab 100 mg with placebo will be reported for inference. If the assumption of Mantel-Fleiss criterion has not been satisfied (less than 5), statistical comparison will be based on GLMM model with treatment group, stratification factors, i.e., body weight class (≤90 kg or >90 kg) and prior exposure to TNF-alpha inhibitors (Yes/No) for psoriasis, visit, treatment group by visit interaction and subjects as the random effect. An unstructured covariance matrix will be used to fit such model. In case, if the model fails to converge, a covariance structure such as compound symmetry or autoregressive model may be used. (PROC GLIMMIX with logit link for logistic regression model).

| Effective Date: 10-AUG-2020 | Page 31 of 61 |
|-----------------------------|---------------|

Observed data after the occurrence of an intercurrent event (ICE) through Week 28 will be handled as a non-responder. Missing values will be imputed using non-responder imputation (NRI). This method corresponds to a composite strategy.

The same analysis will also be conducted for ITT and PP as additional supportive analysis using Observed Cases (OC) where all observed data regardless of the occurrence of any ICE will be included in the analysis as is.

Sensitivity analyses of the primary efficacy endpoint are described in Section 9.3 below.

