9.2.3 Analysis of Secondary Efficacy Endpoints

Binary endpoints

The following binary endpoints will be analyzed in a similar manner as the primary efficacy endpoint based on the analysis population specified in Table 5 in Section 9. A CMH test (rather than M-N methodology) will be used, stratified by prior use of TNF-alpha inhibitors (yes or no) and baseline body weight class (≤90 kg or >90 kg).

- ViSENPsO response at Week 28 (key secondary endpoint)
- ≥ 3-point decrease in Nail Pain NRS score from Baseline at Week 28 in subjects with baseline nail pain NRS score of ≥ 3
- mNAPSI90 at Week 28
- mNAPSI100 at Week 28
- NAPSI75 at Week 28
- NAPSI90 at Week 28
- NAPSI100 at Week 28
- PASI 75 at Week 28
- PASI 90 at Week 28
- PASI 100 at Week 28
- PGA-S response at Week 28

| Effe | ective Date: 10-AUG-2020 | Page | e 35 of 61 |
|------|--------------------------|------|------------|

• 30% decrease in Nail Pain NRS score from Baseline at Week 28 in subjects with baseline nail pain NRS score of ≥3

Continuous endpoints

Change from baseline to week 28 in total-fingernail mNAPSI and total-fingernail NAPSI scores (endpoints included in the hierarchical order of Section 4.5) during the double-blinded period will be analyzed based on the ITT population using MI to handle missing data.

MI procedures for continuous efficacy endpoint (total-fingernail mNAPSI and total-fingernail NAPSI scores):

Missing post-baseline total-fingernail mNAPSI or NAPSI scores through Week 28 will be imputed for the ITT separately for each treatment group using the Markov Chain Monte Carlo (MCMC) method. 50 copies of the dataset with monotonic missing pattern will be generated. For each of the 50 datasets, missing values at scheduled visits (Weeks 4, 8, 12, 16, 20, 24, and 28) will be imputed using a monotone regression model including treatment, presence of TNF-alpha inhibitors at baseline (yes or no), baseline body weight class (≤90 kg or >90 kg), baseline mNAPSI or NAPSI score, and mNAPSI or NAPSI scores at the previous scheduled visits. Change from baseline in mNAPSI or NAPSI score will be derived based on the imputed datasets.

Once imputations are made, the week 28 data of each of the 50 complete datasets will be

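### SAP 9.2.3 sets aside the Miettinen-Nurminen difference and 95% CI that the protocol specifies for the key secondary and other binary secondary endpoints, and the readable SAP names no substitute

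*SAP*

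**What the plan says.** **Protocol.** The synopsis, under statistical methods, states: "Both the primary and key secondary efficacy endpoints will be analyzed using the Cochran-Mantel-Haenszel (CMH) test", with prior TNF-alpha inhibitor use and baseline body weight as strata. It then adds an M-N risk difference and 95% CI. Table 6 in Section 9.4.1 repeats this for the primary and key secondary endpoints together: "M&N common risk (the response rate) difference between tildrakizumab 100 mg and placebo arm along with the 95% confidence interval will be estimated". For the remaining endpoints the same table says: "Binary endpoints up to Week 28 will be analyzed based on the methods described for the primary endpoint".

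**SAP, primary endpoint (9.1.3).** The two methods have separate jobs. For estimation: "Common proportion difference between the treatments and the associated 95% confidence interval will be calculated using Miettinen-Nurminen (M-N"), stratified by the same two factors. For testing: "The p-value from the CMH test comparing tildrakizumab 100 mg with placebo will be reported for inference".

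**SAP, binary secondary endpoints (9.2.3).** The paragraph opens: "The following binary endpoints will be analyzed in a similar manner as the primary efficacy endpoint". The next sentence reads: "A CMH test (rather than M-N methodology) will be used", with the same strata. The list that follows begins with "ViSENPsO response at Week 28 (key secondary endpoint"). It continues with 11 more: two nail pain responder definitions, mNAPSI 90 and 100, NAPSI 75, 90 and 100, PASI 75, 90 and 100, and PGA-S response.

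**Precedence.** SAP Section 1 says that the SAP overrides the protocol's statistical section where needed, and that substantial differences will be flagged in the SAP.

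**The concern.** In this plan the CMH test says whether the arms differ, and the M-N calculation says by how much and how precisely. Setting M-N aside for the secondary endpoints leaves the first answer and takes away the second.

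This matters most for ViSENPsO response. It is the only secondary endpoint labelled key, it is formally tested after the primary, and it is measured on a new scale that is being validated in this same trial. Because the SAP takes precedence, a programmer following 9.2.3 literally would omit an output that the protocol specifies. An interval added later would be chosen after unblinding, and with sparse counts different interval methods give visibly different limits.

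**Working it through.** **Step 1. Set the passages side by side.**

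| Endpoint | Protocol (synopsis, Table 6) | SAP |
|---|---|---|
| Primary, mNAPSI 75 | CMH test, plus M-N difference and 95% CI | 9.1.3: the same |
| Key secondary, ViSENPsO response | CMH test, plus M-N difference and 95% CI | 9.2.3: CMH, M-N set aside |
| 11 other binary secondary endpoints at Week 28 | As for the primary endpoint | 9.2.3: CMH, M-N set aside |

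The SAP agrees with the protocol on the first row and departs from it on the other two, which cover 1 + 11 = 12 endpoints.

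**Step 2. What can the exclusion of M-N remove?** In 9.1.3 M-N produces only the common difference and its CI. The p-value already comes from CMH. If the Mantel-Fleiss criterion is not met, 9.1.3 moves the comparison to a GLMM, which gives M-N no testing role either. So the exclusion in 9.2.3 cannot be replacing one test by another. What it takes out is the difference and its interval.

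**Step 3. Is a substitute named?** The only sentence in 9.2.3 that promises a treatment difference with 95% CI closes the list of continuous endpoints. No other estimate or interval for the binary secondary endpoints appears in the readable text.

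**Step 4. What does not change?** The plan gives no figure on this point. Its sample size reproduces and does not depend on it. The inputs, from Protocol 9.2, are 35% vs 10%, a pooled Z-test, two-sided alpha 0.05 and 80% power:

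- mean rate = (0.35 + 0.10)/2 = 0.225
- n per arm = [1.960 × √(2 × 0.225 × 0.775) + 0.842 × √(0.35 × 0.65 + 0.10 × 0.90)]² / 0.25² = 42.6, so 43
- with 10% dropout, 43/0.90 = 47.8, so 48 per arm and 96 in total

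**Step 5. Does the choice of interval matter?** The counts below are assumed for illustration, with 48 per arm and strata ignored. The documents give no expected rates for ViSENPsO or the other secondary endpoints.

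| Assumed counts | Difference (points) | M-N 95% CI | Wald 95% CI |
|---|---|---|---|
| 17/48 vs 5/48 | 25.0 | 8.6 to 40.5 | 8.9 to 41.1 |
| 8/48 vs 0/48 | 16.7 | 8.7 to 29.7 | 6.1 to 27.2 |

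At moderate rates the two methods nearly agree. With no placebo responders, which is plausible for the 90% and 100% improvement endpoints, both limits move by about 2.5 points (8.7 − 6.1 = 2.6; 29.7 − 27.2 = 2.5).

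**The case against.** The strongest reply is that loss of all estimation is not shown. A reader might infer that these endpoints would have no pre-specified effect estimate at all, or that the size of the ViSENPsO benefit could not be read from the planned analysis. The documents do not support either reading.

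- **Unreadable parts.** SAP Section 9 says that Table 5 gives the statistical models for all efficacy endpoints, but its body is not visible. Nor are the details of the key secondary estimand (9.2.1), Section 12 on changes from the protocol, or the Section 15 code. Any of these could name an estimate or declare the change.
- **CMH procedures can estimate.** The test itself yields a p-value, but the CMH option in SAS can also print Mantel-Haenszel common estimates with limits. The sentence might mean that such an estimate replaces M-N.
- **Descriptive summaries remain.** Section 9 plans summaries of efficacy endpoints by arm and visit, so response proportions and a crude difference would be available.
- **Other wording points towards a shared method.** The opening of 9.2.3 ties these endpoints to the primary analysis, and 9.4.2 refers to the primary and key secondary endpoints as if they used one method. The author may simply have wanted to stress that the p-value comes from CMH.

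All four points limit the size of the concern, but they do not remove it. A Mantel-Haenszel estimate would still depart from the protocol and would need naming. A crude difference is not a stratified difference with an interval. The opening of 9.2.3 does not cancel the specific exception in the next sentence, so the paragraph at best contradicts itself.

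**Conclusion.** The conflict stands in limited form. SAP 9.2.3 sets aside the M-N difference and 95% CI for the key secondary endpoint and the 11 other binary secondary endpoints listed there. That contradicts the protocol synopsis and Table 6, and it sits badly with the SAP's own reference back to the primary analysis. What is lost, on the readable text, is the pre-specified stratified difference and its interval. This is an estimation and reporting matter. The CMH p-value, the testing sequence, type I error and power are untouched.

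Two further inferences should be resisted. The scope is not every binary endpoint in the trial: exploratory endpoints are mainly descriptive under 9.4.2. Nor is the trial's precision a measure of the defect. At 48 per arm and 35% vs 10%, the Wald half-width is 1.96 × √(0.35 × 0.65/48 + 0.10 × 0.90/48) = 0.159, or about 16 points. That is an unstratified figure at the mNAPSI 75 planning rates, and it is the same whichever way the SAP is worded.

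The conclusion assumes that the unreadable SAP parts do not already name an interval or record the change. If they do, 9.2.3 still needs to be brought into line with them.

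**What to change.** In SAP 9.2.3, delete the parenthesis that excludes M-N. State that, for each binary endpoint listed there, the stratified CMH test gives the p-value and the stratified M-N risk difference with 95% CI is reported alongside it, as in SAP 9.1.3 and protocol Table 6. If a different estimate or interval is intended, name it in 9.2.3, make Table 5 and the Section 15 code agree, and record it in Section 12 as a change from the protocol. Either way, settle it before unblinding.

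The cost is a sentence or two of SAP wording. The method is already specified for the primary endpoint, so the same programming can be reused. Sample size, data collection and the testing order do not change.

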4.1.1 PART 1: Double-blind Placebo-controlled (Day 1 to Week 28)

After a Screening Period of up to 28 days and on Day 1, all eligible subjects will be randomized

1:1 to receive either tildrakizumab 100 mg or placebo administered by SC injection on Week 0 (Day 1), Week 4, and Week 16. Subjects should receive the first dose of study treatment within 24 hours of randomization. The treatment period for the double-blind, placebo-controlled part of the study is 28 weeks.

Early Escape: At Week 16, subjects who experience significant worsening of plaque psoriasis (defined as an increase in s-PGA by at least 2 from the baseline measurement) will be eligible for an early escape. (Appendix 20) Subjects selected for early escape by the Principal Investigator at Week 16 will have study medication discontinued and will complete the End of Treatment visit

assessment, followed by the observational safety follow-up period. Subjects entering early escape may be replaced so as to meet the planned evaluable sample size goal for the primary endpoint analysis.

An interim analysis may be performed that could include an unblinded sample size re-estimation (SSRE). The sample size of the study could be increased as a result of this SSRE. In the event of an increase in sample size, the total sample size of the study will not exceed a total of approximately 282 randomized subjects.

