After Week 52 (or early termination of study treatment prior to Week 52), the study treatment should be stopped and all subjects, including those who terminated early from Part 1 and 2 will enter the 20-week Observational Safety Follow-up period to monitor safety and tolerability for 20 weeks following the last dose of study treatment. During the follow-up period, subjects should continue on study-approved concomitant medications only, however, may be placed on appropriate therapies for safety concerns or significant worsening of

| Effective Date: 10-AUG-2020 | Page 10 of 61 |
|-----------------------------|---------------|

psoriasis based on the judgment of the Investigator. The subjects will not receive study treatment during the follow-up period.

Subjects who withdraw from the study will undergo the assessment that corresponds to the last assessment of the study part from which they are leaving. Subjects discontinued from study treatment at any time (apart from withdrawal of informed consent) will complete the EoT (Week 52) assessment approximately 4 weeks after the last dose of study treatment and enter the 20-week Observational Safety Follow-up. Subjects who withdraw from the study during Part 3 will undergo the Week 72 (End of Study [EoS]) assessments approximately 4 weeks after their last visit.

All assessments of safety in PART 3 are scheduled to happen after the date of injection at Week 52. The analysis of efficacy and safety endpoints for PART 3 will follow the analysis visit window and definitions as specified in the sections below.

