3.3 Analysis Time points

Unless specified otherwise, efficacy and safety endpoints will be analyzed according to their scheduled study visits; unscheduled and early termination visits will be mapped to windowed analysis visits defined by actual study day as in table 1.1 below. If there is no evaluation available from the scheduled study visit, and more than one non-missing evaluation is assigned to an analysis window, the evaluation closest to the target day will be used for the analysis. If the two visits are equidistant from the target day, the earlier visit will be used. For early terminated patients, Part 3 is to start the day of last assessment after the last injection plus 28 days.

The following analysis visit windows will apply:

Table 1.1 Analysis Visit Windows

For: ViSENPsO, NAPSI, mNAPSI, PGA-S, BSA, PASI, and C-SSRS

| Derived Visit | Week | Target Day | Analysis Window |
|---|------|------------|-----------------|
| Part 1: Double-blind Placebo-controlled | | | |

| Effective Date: 10-AUG-2020 | Page 17 of 61 |
|-----------------------------|---------------|

| | _ |
|--|---|
| | |

| _ | |
|-----------------------------|---------------|
| Effective Date: 10-AUG-2020 | Page 18 of 61 |

In particular, NRS pain score will be recorded daily in patient diary for the 7 days leading up to each scheduled visit. The analysis visit for NRS will be assigned the same as for the subsequent visit according to Table 1.1, ie, as 7 consecutive days prior to that visit. In the event of a missed visit, the available NRS scores will be mapped to an analysis visit according to Table 1.1, using the last diary entry date as anchor. Any NRS entries outside of the 7-day window will be excluded from the calculation of average NRS. At least 4 out of the 7 daily records are required to calculation of average.

All other assessments (ECG, laboratory data) will be analyzed according to the assigned (nominal) visit unless otherwise specified.

[figure not shown]
For any events/assessments on or after the first administration of study drug, study day is calculated as: event/assessment date – date of first administration of study drug + 1. As such, Day 1 is defined as the date of first administration of study drug.

For any events/assessments before the first administration date, study day is calculated as event/assessment date – date of first administration of study drug.

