4 STATISTICAL / ANALYTICAL ISSUES

4.1 Handling of Dropouts or Missing Data

Data from subjects who withdraw from the study, including AEs and any follow-up, will be included in the analyses as applicable.

For all primary and supportive/sensitivity analyses (including analyses based on Observed Cases [OC]) described below, subjects with missing primary or key secondary efficacy endpoint baseline data will have baseline values imputed as the median of other subjects' non-missing baseline values, considering the analysis set used for the primary analysis (i.e., ITT).

Missing post-baseline data will be handled as per specifications detailed below.

For dichotomized primary and secondary endpoints, subjects with missing data will be imputed using non-responder imputation (NRI) unless noted below and in Table 5 from Section 9.

In addition, sensitivity analyses using last-observation-carried forward (LOCF) (for primary and key secondary efficacy endpoints), and multiple imputation (MI) including a tipping point analysis (for primary and key secondary efficacy endpoints) will be conducted using the ITT set as appropriate. The details are as follows:

- Last observation carried forward (LOCF): The last observed value will be carried forward for any subsequent missing values for endpoints through Week 28. Baseline values will not be carried forward to post-Baseline visits.
- Multiple Imputation (MI): Multiple imputations is a simulation-based approach where missing values are replaced by multiple Bayesian draws from the conditional distribution

| Effective Date: 10-AUG-2020 | Page 21 of 61 |
|-----------------------------|---------------|

of missing data given the observed data and covariates, creating multiple completed data sets. These completed datasets can then be analyzed using standard analysis methods. Details of the imputation model as well as the tipping point analysis are provided in Section 9.3.

[figure not shown]
Continuous efficacy endpoints up to Week 28 will be analyzed with ANCOVA and MMRM under a Missing at Random (MAR) assumption with no imputation.

A summary of the imputation methods for all efficacy endpoints are shown in Table 5 in Section 9.

All safety endpoints will be analyzed as observed cases (OC) in SAF. No other imputation will be used unless otherwise specified.

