analyzed using the ANCOVA model with treatment, randomization stratification factors (prior use of TNF-alpha inhibitors (yes or no), Baseline body weight class (≤90 kg or >90 kg)), and baseline value of the relevant endpoint included in the model, and the SAS MIANALYZE procedure will be used to generate valid statistical inferences by combining results from the 50 analyses using Rubin's formula.

NAPSI scores will be imputed using the same method as mNAPSI as stated above with replacement of mNAPSI with NAPSI in the imputation model.

Example SAS code is provided in Section 15.

Change from baseline to week 28 in other continuous endpoints (nail pain NRS and total BSA) during the double-blinded period will be analyzed based on the ITT population using OC.

All continuous endpoints will be analyzed using an analysis of covariance (ANCOVA) model with treatment, randomization stratification factors (prior use of TNF-alpha inhibitors (yes or no), Baseline body weight class (≤90 kg or >90 kg)), and baseline value of the relevant endpoint included in the model.

Additionally as supportive analysis, they will also be analyzed based on the ITT population for OC using a mixed model for repeated measures (MMRM) procedure that includes fixed effects for treatment, visit, treatment by visit interaction, prior use of TNF-alpha inhibitors

[figure not shown]
| Effective Date: 10-AUG-2020 | Page 36 of 61 |
|-----------------------------|---------------|

Effective Date: 10-AUG-2020

[figure not shown]
(yes or no), Baseline body weight class (≤90 kg or >90 kg), and baseline value of the relevant endpoint as a covariate, comparing the change from Baseline between tildrakizumab arm and placebo arm (refer to Section 15 15 for MMRM procedures).

- Mean change in nail pain NRS score from Baseline at Week 28
- Mean change in total-fingernail mNAPSI score from Baseline at Week 28
- Mean change in total-fingernail NAPSI score from Baseline at Week 28
- Mean percentage change in total BSA involvement from Baseline to Week 28

Treatment difference between tildrakizumab arm and placebo arm will be reported, along with the associated 95% CI and p-value.

Page 37 of 61

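### For nail pain NRS and BSA, leading with the MMRM already planned, instead of the observed-case Week 28 ANCOVA, is a minor improvement at almost no cost

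*SAP*

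**What the plan says.** SAP 9.2.3 treats the continuous secondary endpoints in two groups. Change in total-fingernail mNAPSI and NAPSI ("endpoints included in the hierarchical order of Section 4.5") is multiply imputed from earlier visits and then analysed by ANCOVA. The second group has no imputation; its Week 28 change scores are covered by the words "in other continuous endpoints (nail pain NRS and total BSA) during the double-blinded period will be analyzed based on the ITT population using OC". The model is again ANCOVA, adjusted for the two stratification factors and the baseline value. The repeated-measures model comes second: "Additionally as supportive analysis, they will also be analyzed based on the ITT population for OC using a mixed model for repeated measures".

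SAP 4.1 gives the missing-data assumption: "Continuous efficacy endpoints up to Week 28 will be analyzed with ANCOVA and MMRM under a Missing at Random (MAR) assumption with no imputation". Protocol Section 9.4.1, Table 6 names a single model, fitted over Weeks 4 to 28: "For change-from-baseline at Week 28 (continuous), secondary efficacy endpoints, MMRM model with treatment". The protocol's Schedule of Activities has pain NRS and BSA collected at every visit from Week 4 to Week 28.

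Three provisions create missing Week 28 values:

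- **Early escape** (protocol 4.1.1): "Subjects selected for early escape by the Principal Investigator at Week 16 will have study medication discontinued". SAP 2.1 says that subjects who stop treatment "will complete the EoT (Week 52) assessment approximately 4 weeks after the last dose of study treatment", and SAP 3.3 says "unscheduled and early termination visits will be mapped to windowed analysis visits defined by actual study day as in table 1.1 below".
- **Diary rule** (SAP 9.2.2): a visit's NRS average needs at least four of seven daily entries.
- **Visits**: protocol 8.0 allows some to be virtual, and SAP 6.2 expects some efficacy assessments not to be done because of COVID-19.

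**The concern.** An ANCOVA on observed Week 28 values, adjusted only for strata and baseline, needs more than the missing-at-random assumption in SAP 4.1. It needs Week 28 missingness to be unrelated to the Week 28 outcome given arm, strata and baseline alone. MMRM may also condition on the observed Week 4 to 24 values, so the stated assumption fits the supportive model better than the lead one.

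Early escape strains the stronger condition because exit depends on post-baseline skin status. If exits are mostly on placebo, the worst placebo subjects disappear from the Week 28 comparison and the difference shrinks toward zero. Missing diary averages mainly cost precision, because subjects with seven visits of data contribute nothing when the last average fails the four-of-seven rule.

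The stakes are small. Protocol 9.4 and SAP 4.5 appear to make these comparisons descriptive, and both models will be run. The choice decides which estimate, interval and p-value lead.

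**Working it through.** **1. The plan's own size.** Protocol 9.2 assumes 35% vs 10%, two-sided alpha 0.05, 80% power and a pooled Z-test. With mean proportion 0.225:

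n = [1.96·√(2·0.225·0.775) + 0.8416·√(0.35·0.65 + 0.10·0.90)]² / 0.25² = (1.157 + 0.474)² / 0.0625 = 42.6, so 43 per arm (power 80.4%).

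43/0.90 = 47.8, so 48 per arm. The plan's figures reproduce. It gives no SD, correlation or power for NRS or BSA, so all inputs below are assumptions.

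**2. Where an escaper's last value falls.** Week 16 is Day 16×7+1 = 113 and Week 28 is Day 197. The end-of-treatment assessment falls between Day 113 (at the escape visit) and Day 113+28 = 141 (four weeks after a Week 16 dose). That is 84 to 56 days before Day 197, with Week 20 (Day 141) and Week 24 (Day 169) nearer. Escapers therefore appear to have no Week 28 value, although the window limits in SAP Table 1.1 are not visible.

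**3. Bias from escape.** This is a closed form for selection on a latent Week 16 s-PGA. On the 0–5 scale with entry at 3 or more, only a baseline of 3 can rise by 2; 60% are assumed to be there. Treatment shifts the latent score by 1 SD, and the Week 16–28 outcome correlation is 0.5–0.7. The target is the value had the subject not escaped. Placebo escape of 1%, 2% and 5% is about 0.5, 1 and 2.4 of 48 subjects. Bias as % of the assumed effect:

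| | 1% | 2% | 5% |
|---|---|---|---|
| NRS, ANCOVA | 0.3–1.1 | 0.5–2.0 | 1.0–4.0 |
| NRS, MMRM | 0–0.6 | 0–1.0 | 0–2.0 |
| BSA, ANCOVA | 0.5–1.4 | 0.8–2.5 | 1.7–5.0 |
| BSA, MMRM | 0–0.7 | 0–1.2 | 0–2.5 |

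For NRS the assumed difference is −2.0, SD 2.4, correlation with s-PGA 0.2–0.4. For BSA percent change it is −40, SD 40, correlation 0.4–0.6. The largest ANCOVA biases are 4.0% × 2.0 = 0.08 NRS points (0.15 SE) and 5.0% × 40 = 2.0 BSA points (0.23 SE). MMRM removes 50–100%. It need not remove all, because s-PGA is not in the model.

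**4. A second calculation.** This simulated 450 trials per scenario, 48 per arm, seven visits, NRS SD 2.5 and 10% dropout related to poor response.

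- NRS (true effect −1.25): ANCOVA bias 0.010–0.048 (0.8–3.8%), MMRM 0.003–0.025.
- BSA (true effect −68.9): ANCOVA bias 1.6–4.6 (2–7%), MMRM 0.2–1.6.
- With completely random dropout there is no bias to remove.

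**5. Precision.** Let d be the share missing at Week 28 and R² the share of residual Week 28 variance explained by earlier visits. Then SE(MMRM)/SE(ANCOVA) = √[(1−d)/((1−d)+d·R²)].

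- d = 0.10: √(0.90/0.92) = 0.989 at R² = 0.2; √(0.90/0.98) = 0.958 at R² = 0.8; limit √0.90 = 0.949.
- d = 0.20: 0.976 at R² = 0.2 and 0.913 at R² = 0.8.

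Simulated model-based SE, using the SAP's MMRM terms with unstructured covariance assumed:

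- NRS, 10% dropout, second simulation: ratio 0.983–0.996. A further simulation (SD 2.4) gave an SE 1–2.5% smaller at 6–10% missing.
- NRS, no diary loss, 8% missing (1,000 replicates, 48 per arm): gain under 0.5%.
- NRS, 10% diary loss plus dropout (17–18% missing): 0.540–0.550 for ANCOVA and 0.514–0.530 for MMRM, or 2.7–4.8% smaller. As information, 1/0.973² to 1/0.952² is 6–10% more, like 5–8 of about 79 evaluable subjects.
- BSA: 8.50 vs 8.41, about 1%.

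The realised gain is smaller. With diary loss, RMSE was 0.538–0.556 for ANCOVA and 0.520–0.544 for MMRM, about 2–3% lower. At 10% dropout the second simulation's empirical NRS SE ratio was 0.99–1.02, because the SAP's MMRM has no baseline-by-visit term; adding one gave 0.96–0.99. The further simulation's empirical gain at planned dropout was nil to 4%.

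**6. Coverage.** ANCOVA 93.8–95.3%, MMRM 94.3–95.5%. The swap costs none.

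**The case against.** The best counter-argument is that protocol 8.1.4 and SAP 3.2 base the NRS analysis on the change in averaged scores between Baseline and Week 28, which reads naturally as a Week 28 ANCOVA. SAP Section 1 also lets the SAP override the protocol, so departing from Table 6 is permitted. Neither point defeats the change. The MMRM Week 28 contrast is still a change between those two averages, it imputes no diary day, and protocol 8.1.4 leaves the detail to the SAP. No undeclared departure is alleged, since SAP Table 5 and Section 12 are not visible.

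Several limits do stand:

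- Nothing confirmatory appears to depend on the order.
- The larger precision gain needs an assumed 10% diary loss, and is smaller if the loss clusters in poor compliers.
- At planned dropout the realised NRS gain may be nil.
- The escape rate is undocumented, and the bias is toward the null, so it does not flatter the drug.
- No estimand for these endpoints is visible.
- NRS and BSA would have a different lead model from mNAPSI and NAPSI, although those already borrow from earlier visits through imputation.
- SAP Section 15 holds the MMRM procedure and cannot be read here, so its covariance structure and convergence fallback need confirming before it leads.

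**Conclusion.** The point holds as a minor, optional improvement. The lead analysis for NRS and BSA discards Week 4 to 24 data that a model already in the same section would use, and it needs a stronger missing-data assumption than the SAP states.

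The ANCOVA bias is at most about 4% of the NRS effect and 5–7% of the BSA effect across the two sets of assumptions, and MMRM removes about half of it or more. The reported NRS standard error is slightly smaller: at most about 2.5% near planned dropout, and about 3–5% with 10% diary loss. For BSA, or for NRS with complete diaries, the precision gain is close to nil. All of this rests on assumed SDs, correlations, escape rates and dropout mechanisms.

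Separately, the exclusion of imputation in SAP 4.1 does not match the multiple imputation of mNAPSI and NAPSI in 9.2.3. That is a wording point only.

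**What to change.** In SAP 9.2.3, write:

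> Change from baseline to Week 28 in nail pain NRS and percentage change in total BSA will be analyzed in the ITT population with the MMRM described below, using all observed visits through Week 28. The Week 28 treatment contrast is the main result. ANCOVA on observed Week 28 values is supportive.

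In SAP 4.1, replace the blanket statement with:

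> No imputation, except for change in total-fingernail mNAPSI and NAPSI, which use the multiple imputation in Section 9.2.3.

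Put the models in the same order in Table 5. Keep the MMRM procedure referred to in Section 15, after checking that it states the covariance structure and a fallback.

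The cost is two SAP passages and one table entry, made before unblinding. Both models are already specified on the same data, so no new data, model or programming is needed.
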